5.1.1.3 Protocol Deviations

Important protocol deviations (IPDs) are deviations from the protocol which potentially could have a meaningful impact on the study conduct or on the primary efficacy, key safety, or PK/PD outcomes (if applicable) for an individual participant. IPDs will be reviewed as part of the ongoing data cleaning process and data evaluation. IPDs will be identified and documented prior to unblinding and will be utilized to decide which data will exclude study participants from the PPS and PK-PPS.

Analysis related to protocol deviations is described in Section [6.1.2](#).

5.1.1.4 Treatment assignment and treatment groups

SS and SS_{NO}COVID-19 analyses will be based on the actual treatment received.

- If after unblinding it is determined that participants at any time received incorrect treatment as compared to the one they were randomized to, then these participants will be reallocated to the appropriate IMP. For example, if participants randomized to placebo received Zilucoplan, then for the safety and PK/PD analyses, these participants will be reallocated to Zilucoplan. Participants randomized to Zilucoplan will only be reallocated to the placebo IMP if they never received Zilucoplan. Placebo
- 0.3 mg/kg Zilucoplan
- All participants (if appropriate)

For specific safety analysis, data from the Main and the Extension Portion will be combined and summarized. Specifically, safety data of participants who received Zilucoplan 0.3 mg/kg during the Main Portion of the study will be combined with the Extension Portion safety data.

Efficacy data during the Extension Portion will be shown based on the combination of the randomized and treatment switch:

- Placebo - 0.3 mg/kg Zilucoplan
- 0.3 mg/kg Zilucoplan - 0.3 mg/kg Zilucoplan.

Following to the analysis of Week 8 Main Portion of the study, re-alignment based on duration of medication exposure might be considered if deemed necessary.

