12.1.3 SAFETY POPULATION

The Safety Population will include all subjects who have received at least 1 dose of study drug, with subjects to be analyzed based on the actual treatment received.

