4 POPULATIONS FOR ANALYSIS

- **Enrolled Set (ES):** will include in all screened participants including screen failures.
- **Intention-to-Treat Population (ITT):** will include all randomized participants.
- **ITT_{NoCOVID-19}:** will include all ITT participants excluding those with confirmed COVID-19 as observed during any visit of the Main Portion of the study and reported in the AE eCRF form.

Of note, ITT_{NoCOVID-19} will be considered in any analysis specified in the current document during the Main Portion only, provided it differs by at least 15% from the ITT in terms of number of participants.

- **Per Protocol Set (PPS):** will include all participants in the ITT Population who have completed the 8 Week Treatment Period and have no important protocol deviations. Important protocol deviations will be evaluated during ongoing data cleaning meetings prior to unblinding of the data.

If a participant received multiple doses of different study drug (i.e., placebo and 0.3 mg/kg), the patient will be assigned to the dose group which they received at the highest frequency within the Main Portion of the study.

- **Intention to Treat - Extension (ITT_{EXT}):** will include all participants who entered the Extension Portion of the study.
- **Safety Set (SS):** will include all participants who received at least 1 dose of study drug during the Main Portion of the study irrespective if they continued to the Extension Portion. Participants will be analyzed based on the actual treatment received.

If a study participant received multiple doses of different study drug (i.e., placebo and 0.3 mg/kg), the participant will be assigned to the dose group which he/she received at the highest frequency within the Main Portion of the study.

Of note, participants who were on placebo during the Main Portion of the study and continued to the Extension Portion will be included in both groups depending on the study period assessed. Safety results on 0.3 mg/kg across the Main and Extension Portions will be combined.

- **Safety Set No Covid-19 (SSNOCOVID-19):** will include all participants in the SS except those with confirmed COVID-19 (as reported in AE eCRF form) during any time of the study (Main or Extension Portion).
Of note, SSNOCOVID-19 will be considered in any analysis specified in the current document, provided it differs by at least 15% from the ITT in terms of number of participants.

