5.6.2 Adverse Events

Adverse events will be captured from the time of informed consent signature (only the SAEs) or from the time of first administration (Treatment Emergent Adverse Events) and will be reported if occurred during scheduled or unscheduled visits. As Treatment Emergent AE (TEAE) is defined as an AE starting on or after the time of first administration of study drug or an AE that increases in severity after treatment start, if the event was present at the time of the treatment initiation. Reporting of TEAEs refer to the period until the administration of the last study dose plus 40 days (or last visit depending which occurs first).

AEs will be classified according to the Common Terminology Criteria for Adverse Events (CTCAE) Version 5.0 for severity. For any AE where it is not possible to provide a CTCAE grading, the event will be assessed using a standard intensity classification (mild, moderate and severe). For the purpose of the tabulations all CTCAE severity classifications will be mapped to a mild/moderate/severe grade as described below:

- Grade 1 - Mild
- Grade 2 - Moderate
- Grade 3, 4, 5 - Severe

These will be tabulated together with the AEs that were not classified according to CTCAE criteria i.e., all Grade 1 AEs as per CTCAE criteria will be included in the ‘mild’ category together with those AEs classified as mild as per the ‘standard’ intensity classification.

If a particular AE severity is missing, then this will be listed as missing and treated as missing in summaries. If a participant has experienced more than one TEAE within the same PT, then the AE with the greatest severity will be presented. If a participant reported more than one AE within the same (System Organ Class) SOC then the participant will be counted only once with the greatest severity at the SOC where applicable.

Where dates are missing or partially missing, AEs will be assumed to be treatment-emergent unless evidence exists that does not allow the AE to be treatment-emergent. Handling of missing dates for classification of AEs as TEAEs is described in Section 5.1.1.8.

TEAE summaries will be performed in SS and repeated in SS_{NOCOVID-19} if at least 15% of the participants have at least one AE as ‘Confirmed COVID-19’.

Summaries may also be repeated in SS among participants with at least one TEAT based on the COVID-19 period defined as:

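### SAP Sections 4 and 5.1.1.4 give different rules for placing a Safety Set participant who received both placebo and zilucoplan in the Main Portion

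*SAP*

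**What the plan says.** Two places in the SAP decide the treatment column of a Safety Set participant who received both treatments.

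- **SAP Section 4, Safety Set.** For someone given both treatments, the rule reads: "the participant will be assigned to the dose group which he/she received at the highest frequency within the Main Portion of the study".
- **SAP Section 5.1.1.4.** For the Safety Set and its version without COVID-19 cases, "analyses will be based on the actual treatment received". The rule applies when "participants at any time received incorrect treatment as compared to the one they were randomized to". For the placebo arm: "if participants randomized to placebo received Zilucoplan, then for the safety and PK/PD analyses, these participants will be reallocated to Zilucoplan". For the zilucoplan arm: "Participants randomized to Zilucoplan will only be reallocated to the placebo IMP if they never received Zilucoplan".

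Protocol Section 12.1.3 defines the Safety Population "with subjects to be analyzed based on the actual treatment received" and has no rule for mixed exposure. SAP Section 5.6.2 states that "TEAE summaries will be performed in SS", and TEAE incidence is the primary safety endpoint (SAP Table 1-1). SAP Section 4 draws the PK and PD per-protocol sets from the Safety Set. SAP Section 5.6.1 has a third treatment of the same people: for exposure, a participant with both treatments is shown under each, split by start and stop dates.

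**The concern.** The two rules cover the same set and the same event, and no text says which prevails. For a participant with a minority of zilucoplan doses, the Section 4 rule counts events that followed real zilucoplan exposure as placebo events.

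The assignment feeds the TEAE tables and, through the PK and PD sets, the comparison of active with placebo on the PD endpoints (SAP Section 5.7.1.2). Section 5.1.1.4 provides for mis-dosing that is established after unblinding. With two written rules, the choice between them could then be made with treatment codes and events in view, which prespecification is meant to prevent.

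**Working it through.** The plan gives no figure to reproduce here. The check applies both rules to every possible mix of doses and then sizes the effect of moving one participant.

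**Inputs**
- Main Portion dosing: daily, Day 1 to Day 57 (Protocol 7.2.2). This is n = 57 blinded doses if the Day 57 dose counts, and n = 56 if not.
- Kits of 7 syringes (Protocol 9.2.2), with syringes dispensed at each study visit (Protocol 9.2.1).
- 12 participants per arm (SAP 1.2).
- b = number of other participants with a TEAE in each arm. The documents give no rate, so b = 0, 3 and 6 are assumptions.

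**Where the rules disagree.** Let k be the number of zilucoplan doses among n.
- Section 4: zilucoplan if k > n − k, placebo if k < n − k, undefined if k = n − k.
- Section 5.1.1.4: zilucoplan if k ≥ 1, for either randomized arm.
- They therefore disagree for 1 ≤ k < n/2.
  - n = 57: k = 1 to 28, which is 28 of the 56 mixed patterns.
  - n = 56: k = 1 to 27, which is 27 of the 55 mixed patterns. At k = 28 Section 4 has no answer.
- In every disagreement Section 4 gives placebo and Section 5.1.1.4 gives zilucoplan. The reverse never occurs.

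For example, one wrong 7-syringe zilucoplan kit given to a placebo participant makes k = 7 of 56. Section 4 gives placebo and Section 5.1.1.4 gives zilucoplan.

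**Effect of moving one participant.** Take a placebo-randomized participant who has a TEAE. Section 4 leaves the arms at 12 and 12. Section 5.1.1.4 makes them 11 and 13.
- Fall in placebo incidence: (b+1)/12 − b/11 = (11 − b)/132.
- Rise in zilucoplan incidence: (b+1)/13 − b/12 = (12 − b)/156.

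| b | Section 4: placebo vs zilucoplan | Section 5.1.1.4: placebo vs zilucoplan | Placebo falls by | Zilucoplan rises by |
|---|---|---|---|---|
| 0 | 1/12 = 8.3% vs 0/12 = 0% | 0/11 = 0% vs 1/13 = 7.7% | 8.3 points | 7.7 points |
| 3 | 4/12 = 33.3% vs 3/12 = 25.0% | 3/11 = 27.3% vs 4/13 = 30.8% | 6.1 points | 5.8 points |
| 6 | 7/12 = 58.3% vs 6/12 = 50.0% | 6/11 = 54.5% vs 7/13 = 53.8% | 3.8 points | 3.8 points |

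Under Section 5.1.1.4 the difference, zilucoplan minus placebo, is (b+1)/13 − b/11 = (11 − 2b)/143. It is positive for b up to 5. Under Section 4 it is always −1/12. The direction of the comparison therefore reverses at b = 0 and b = 3. At b = 6 it does not; the gap narrows from 8.3 to 0.7 points.

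If the moved participant has no TEAE, only the denominators change: placebo rises by b/132 and zilucoplan falls by b/156, which at b = 3 is 2.3 and 1.9 points.

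**The case against.** **The rules can be reconciled.** Section 5.1.1.4 speaks of reallocation to the appropriate product, which might defer to Section 4, and its placebo case is only an example, perhaps of someone wholly mis-assigned. This fails on the sentence about the zilucoplan arm. A participant randomized to zilucoplan who took mostly placebo is placebo under Section 4, but cannot be moved there under Section 5.1.1.4 because some zilucoplan was received.

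**The effect is contingent.** This stands. The rules agree for everyone who took one treatment throughout, and neither document reports or expects a dispensing error. A reader might infer that every Safety Set table is in doubt; the documents do not support that. Nor is the planned switch from placebo to zilucoplan in the Extension affected: Section 4 handles it separately, by study period.

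**Section 5.1.1.4 has the mirror fault.** This also stands. One stray zilucoplan syringe moves the participant's whole Main Portion, including events that began on placebo before that dose, into the zilucoplan column. Neither rule classifies events by onset date. A reader might infer that the SAP itself marks the Section 4 rule as the wrong one. It does not, and a preference for Section 5.1.1.4 is a judgement about caution.

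**Errors need not surface only after unblinding.** Section 5.1.1.4 is conditional on this point, and Protocol Section 11.5.2 lists medication errors among the special situations to be reported. Post-unblinding discovery is a possibility that the plan provides for, not a certainty.

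**Conclusion.** The SAP contradicts itself on treatment assignment for mixed exposure in the Safety Set, the set that carries the primary safety endpoint. The conflict arises whenever zilucoplan was received but made up the minority of Main Portion doses, and in each such case Section 4 is the rule that gives placebo.

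The point is minor because it needs a dispensing error to have any effect. A reader might take one participant as a fixed 8.3 points of an arm's incidence. That is the ceiling for the placebo arm, reached when no other placebo participant has an event; the zilucoplan ceiling is 7.7. With 3 others per arm affected, the shifts are 6.1 and 5.8 points, enough to reverse the direction of the comparison. These sizes assume 12 per arm, one affected placebo-randomized participant with a TEAE, and equal numbers of other cases in the two arms.

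**What to change.** Before unblinding, state one assignment rule for the Safety Set and its version without COVID-19 cases, and apply it to the PK and PD sets drawn from the Safety Set.

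The cautious choice for drug safety is to keep the any-zilucoplan rule in Section 5.1.1.4 and delete the most-frequent-treatment paragraph from the Safety Set definition in Section 4. The small cost is that events begun on placebo in a mixed-exposure participant count under zilucoplan. The similar paragraph under the Per Protocol Set is not part of this conflict.

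In the same edit, say how the date-split sentence in Section 5.6.1 applies to Main Portion errors. Otherwise exposure could be split by date while TEAEs are assigned wholly to zilucoplan. The change is one deleted paragraph plus short aligning text in Sections 4, 5.1.1.4 and 5.6.1, with no effect on design or data collection.

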5.1.1.5 Center pooling strategy

All centers will be pooled together for the efficacy analysis of this study. **Coding dictionaries**

Adverse events (AEs) and medical history will be coded using the Medical Dictionary for Regulatory Activities (MedDRA®) using the existing version at the date of the database lock. The MedDRA version will be stated at each relevant table.

Medical procedures will not be coded.

Medications will be coded according to the Anatomical Therapeutic Chemical Classification system (ATC) / World Health Organization Drug Dictionary and (WHODD), using the existing version at the date of database lock. The version will be stated at each corresponding table.

5.1.1.7 Multicenter studies

This is a study targeting 24 participants and conducted at 18 sites. No efficacy results will be displayed by study site.

5.1.1.8 Handling of drop outs or missing data

5.1.1.8.1 Missing efficacy data

The rules for handling missing data of individual items in the calculation of the PROs and performance outcomes are described in Section [6.1.5](#).

Main Analysis

- No multiple imputation methodology will be considered with respect to the main analysis of the primary and secondary efficacy objectives.
- If a participant receives prohibited medication, then efficacy data will be censored at the date/time that he/she received the medication.

Sensitivity Analysis

- Trimmed means methodology with imputation at extreme unfavorable value for the primary objective of CK levels (if applicable based on SAP criterion, see Section 5.3.3).

5.1.1.8.2 Missing data due to Covid-19

Missing data is expected to be one of the implications of the COVID-19 pandemic. The following approaches/strategies will be applied to assess the impact of COVID-19 in this study.

- Added an eCRF page “COVID-19 Impact”, including impacted visits, and reasons.
- Additional fields were added in protocol deviation specification documents to record protocol deviations relationship to COVID-19.
- Included additional summary analyses based on the timing of COVID-19 impact (pre or during the COVID-19 pandemic period).
- An overall summary of number of visits impacted by COVID-19 by IMP.
- Summary on numbers of actual visits performed for each nominal visit (along with the summary on the primary reason the assessments were impacted (COVID-19 Precaution Measures / Participant was Diagnosed with COVID-19)).

5.1.1.8.3 Missing dates and times

Partially or completely missing dates may be imputed for the following reasons:

- Classification of AEs as TEAEs;
- Classification of medications as past, prior, or concomitant medications;

Imputed dates will not be shown in listings (dates will be displayed as reported in the database).

The following rules will be applied for partially or completely missing start dates:

- If year, month and day are all missing then assign the date of first dose of study intervention. If an imputed start date is after the specified end date, then assign January 01 of the year of the end date, or the date of screening if this is later (if the latter imputation results in an end date that is earlier than the start date, then use January 01).
- If month and day are missing, and year is:
 - the same as the year of the first dose of IMP then assign the month-day of first dose of IMP. If the imputed start date is after the specified end date, then assign January 01, or the month-day of screening date if this is later (if the latter imputation results in an end date that is earlier than the start date, then assign January 01);

- not the same as the year of the first dose of IMP then assign January 01.
- If only day is missing and month-year is:
 - the same as the month-year of the first dose of IMP then assign the day of first dose of IMP. If the imputed start date is after the specified end date, then assign first day of the month, or the day of screening date if this is later (if the latter imputation results in an end date that is earlier than the start date, then assign first day of the month);
 - not the same as the month-year of the first dose of IMP then assign the first day of the month.

The following rules will be applied for partial stop dates:

- If only the month and year are specified, then use the last day of the month;
- If only the year is specified, then use December 31 of the known year;
- If the stop date is completely unknown, then use discharge date or data cut-off date.

Date of discontinuation, the date of last contact will be used as the discharge date. For participants still ongoing at the time of the data cut-off, and for whom no discharge date is available, the date of the data cut-off will be used instead of the discharge date.

In the event of ambiguity or incomplete data that makes it impossible to determine whether a medication was concomitant, the medication will be considered as concomitant. Similarly, in the event of ambiguity or incomplete data which makes it impossible to determine whether a medication is to be assigned to the Main Portion or to the Extension Portion of the study or both, then the medication will be assigned to both study portions.

The following rules are applied to impute partial onset and resolution dates for AEs. AEs with partial onset date are classified as either non-treatment- or treatment-emergent based on the imputed onset date. The imputed onset date is also used to classify TEAEs by study portion or into time intervals. Each TEAE should be classified into exactly one study portion for the classification of TEAEs into study periods.

Imputation of Partial Onset Dates

- If only the month and year are specified and the month and year of first dose is not the same as the month and year of onset, then use the 1st of the month
- If only the month and year are specified and the month and year of first dose is the same as the month and year of onset, then use the date/time of first dose
- If only the year is specified, and the year of first dose is not the same as the year of onset, then use January 1 of the year of onset
- If only the year is specified, and the year of first dose is the same as the year of onset, then use the date/time of first dose
- If the AE onset date is completely unknown, then use the date of first dose

Imputation of Partial Resolution Dates (if needed)

- If only the month and year are specified, then use the last day of the month
- If only the year is specified, then use December 31 of that year
- If the stop date is completely unknown, then use discharge date or data cut-off date.

Note: Discharge date refers to the date of the end of study visit for completed participants or the date of discontinuation for participants that were withdrawn. For any AEs with known start date after the date of discontinuation, the date of last contact will be used as the discharge date. For participants still ongoing in the study at the time of the data cut-off, and for whom no discharge date is available, the date of the data cut-off will be used instead of the discharge date.

Consequently, AE duration will be calculated as stop date – start date + 1.

In the event of ambiguity or incomplete data that makes it impossible to determine whether an AE was treatment emergent, the AE will be considered treatment emergent. Similarly, in the event of ambiguity or incomplete data which makes it impossible to determine whether an AE is to be assigned to the Main Portion of the study or to the Extension study portion, then the AE will be assigned to the Main Portion.

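### Partial-date rules can drop zilucoplan-period adverse events of placebo crossovers from the combined zilucoplan safety tables

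*SAP*

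**What the plan says.** SAP 5.1.1.8.3 sets three layers of rules for adverse events with incomplete onset.

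- **Imputation.** "If the AE onset date is completely unknown, then use the date of first dose". A year-only onset in the year of first dose, or a month-only onset in the month of first dose, is also set to first dose. Any other month-only date goes to the 1st of that month, and any other year-only date to 1 January.
- **Portion.** "The imputed onset date is also used to classify TEAEs by study portion or into time intervals", and "Each TEAE should be classified into exactly one study portion".
- **Fallback.** This applies where missing information "makes it impossible to determine whether an AE is to be assigned to the Main Portion of the study or to the Extension study portion". The outcome is the same whatever arm the participant was randomised to: "then the AE will be assigned to the Main Portion". There is no exception for participants who change treatment between portions.

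SAP Section 4 makes the portion decide the treatment group: placebo participants who continue "will be included in both groups depending on the study period assessed". It adds: "Safety results on 0.3 mg/kg across the Main and Extension Portions will be combined". SAP 5.6.2 and 5.6.3 then give exposure-adjusted tables over Main and Extension for zilucoplan only. SAP 5.6.1 presents participants exposed to both treatments under each one, using that treatment's own start and stop dates.

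**The concern.** For a participant on zilucoplan throughout, the portion chosen does not alter the treatment to which the event is attributed. For a placebo participant who crosses over, it does. An event that began on zilucoplan but is dated to the Main Portion becomes a placebo event. It then leaves the numerator of the combined zilucoplan tables and has no other column there to appear in, while the participant's time on zilucoplan stays in the denominator.

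These tables carry the longer-term safety account of the drug, including Neisseria infections and the other events of interest. For a rare event, one lost case matters: if it is the only case, the reported rate becomes zero. The same SAP section resolves doubt about treatment emergence by calling the event treatment-emergent. For a crossover participant, Main versus Extension is that same question asked about zilucoplan, and it is resolved the other way. The SAP has no sensitivity analysis for these events.

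**Working it through.** The plan states no figure for this point, so there is none to reproduce. The check traces the rules and counts where they lead.

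**Inputs.** Planned size is 12 placebo participants and 24 in all (SAP 1.2). The first zilucoplan dose for placebo participants is on Day 57/E1 (SAP 5.1.1.2.4). The Extension Period starts the day after the Treatment Period ends, so Day 58 (SAP 5.1.1.2.2). Events map to a portion by onset date (SAP 5.6.2).

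**Assumptions.** First dose means first dose of any study drug. First-dose dates are spread over all 366 days of a leap year. True onset is uniform over the stated number of days after Day 57.

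**Step 1: direction.** An imputed date is either the first dose or the first day of the known month or year. It can never be later than the later of first dose and true onset. A true Main onset therefore cannot be imputed into the Extension (0% in the count). Errors run only from Extension to Main.

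**Step 2: share of true post-crossover onsets imputed to Day 57 or earlier.**

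| Onset within | Month and year known | Year only | Unknown |
|---|---|---|---|
| 28 days | 52% | 96% | 100% |
| 56 days | 26% | 92% | 100% |
| 117 days | 13% | 84% | 100% |
| 180 days | 8% | 75% | 100% |

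Month-only dates go wrong only in the calendar month that contains Day 57. With first dose on 1 July, Day 57 is 26 August. An event that began on 30 August and is recorded only as August is dated 1 August, hence placebo. One recorded only as September is dated 1 September, correctly in the Extension. Year-only dates go wrong more often. With first dose on 1 December, Day 57 is 26 January, and a March event recorded by year alone is dated 1 January, again placebo.

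**Step 3: combined zilucoplan tables.** If all 24 participants receive zilucoplan, losing one participant with an event lowers crude incidence by 1/24 = 4.2 points, two by 2/24 = 8.3 and three by 3/24 = 12.5. In the EAIR the numerator falls by one. Time at risk also rises, because SAP 5.6.2 censors it at the event and the participant now contributes full exposure. The loss applies only where the participant is not otherwise counted for that term.

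**Step 4: Main Portion comparison.** Take assumed true counts of 3/12 on zilucoplan and 1/12 on placebo, a difference of 2/12 = 16.7 points.

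- One placebo participant moved: 3/12 versus 2/12, or 8.3 points.
- One participant moved in each arm: 4/12 versus 2/12, still 16.7 points. The ratio falls from 3 to 2.

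A placebo-only shift is worth up to 1/12 = 8.3 points of placebo incidence, but the rule is not placebo-only.

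**The case against.** A reader might infer that the primary safety comparison is itself tilted towards zilucoplan. The documents do not support that. The imputation and the fallback are the same for both arms, so ambiguous Extension events of zilucoplan-zilucoplan participants are pulled into Main as well. In the Extension everyone is on zilucoplan, so such events should arise in both groups. The result is mainly contamination. Where it dilutes a ratio, it favours whichever arm has more events.

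A reader might also want to move only placebo participants' ambiguous events out of Main. In the Step 4 example that leaves 4/12 versus 1/12, a difference of 25 points against a true 16.7. An arm-specific rule would bias the randomised comparison.

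Further objections stand in part:

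- Exposure to the problem is limited. Protocol 11.4.1.1 asks for date and time of onset, and Protocol Table 2 schedules adverse event review at E1, E8, E15 and E29, when ambiguity matters most. Listings show dates as reported, so cases could be found by hand, though the tables would not reveal them.
- The contrast with medications, which are assigned to both portions when in doubt, is weak. Medication use can span portions, whereas an event has one onset.
- Early imputation also shortens time at risk for zilucoplan-zilucoplan participants, which nudges the EAIR upwards. That is an effect of timing, not attribution, and it restores no lost event.

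None of this answers the loss from the combined tables.

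**Conclusion.** The point holds for the combined Main and Extension zilucoplan tables. There, a stated rule can move crossover participants' zilucoplan-period events to placebo and never the reverse, so through attribution the zilucoplan counts and rates can only be understated. The size is up to 4.2 percentage points of incidence per participant lost, if all 24 receive zilucoplan. How many events will have incomplete dates is not stated; it is probably few and may be none. The shares in Step 2 rest on uniform onset and on reading first dose as first study drug. For the 8-week comparison, the supportable statement is contamination of both arms. The matter is small but directional, and it is cheap to correct before unblinding.

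**What to change.** Keep the common imputation and fallback for the Main Portion comparison. In SAP 5.1.1.8.3, with a cross-reference from 5.6.2 and 5.6.3, add a rule for the combined zilucoplan tables only: *For a placebo participant who received zilucoplan in the Extension, an adverse event is flagged and counted under zilucoplan if its known onset date parts allow onset on or after the first zilucoplan dose and any known stop date does not precede that dose.*

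The assignment must be made by the flag, not by a new imputed date. SAP 5.1.1.2.2 starts the Extension the day after Day 57, so an onset imputed to Day 57/E1 would map back to Main. The flag should also catch a fully dated event that begins on Day 57 after the zilucoplan dose. For time at risk, use the earliest date on or after that dose that the known parts allow. A footnote giving the number of flagged events would show readers how much depends on the rule.

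The cost is one derivation flag and a short SAP addition. The downside is slightly higher zilucoplan counts, possibly including some events that truly began on placebo.
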